**Table 7 - SAR444245 dose reduction criteria**

Actual dose level	Dose level interval
8 µg/kg	
16 µg/kg	
24 µg/kg	

- Dose omission is defined as a dose not administered at the scheduled visit.
- Dose interruption: A dose will be considered as interrupted if SAR444245 administration is stopped during an infusion regardless of whether it is restarted or not.

Dose modifications and dose interruptions will be analyzed by participant and dose as follows:

- **Participant** (number of participants treated will be used as denominator)
  - Number (%) of participants with at least 1 dose modification
    - Number (%) of participants with at least 1 dose reduction
    - Number (%) of participants with at least 1 dose omission
  - Number (%) of participants with at least 1 dose interruption
    - Number (%) of participants with at least 1 dose interrupted and restarted
    - Number (%) of participants with at least 1 dose interrupted and not restarted
  - Number (%) of participants with at least 2 dose interruptions
- **Dose** (number of doses started will be used as denominator)
  - Number of doses
  - Number (%) of dose interruptions
  - Number (%) of doses interrupted and re-started
  - Number (%) of doses interrupted and not re-started
  - Number (%) of doses interrupted more than once,
  - Number (%) of doses interrupted at 1st dose, 2nd dose, subsequent doses,
  - Time from dose start to first interruption in minutes summarized as a continuous variable and by category.

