**Table 1 - Overview of study cohorts**

Substudy	Cohort	Study intervention	Disease
01	A	SAR444245 + pembrolizumab	2-3L ESCC - Regardless of CPS Post-PD1/PDL1
02	B1	SAR444245 + pembrolizumab	1-3L GC/GEJ non-MSI-H CPS $\geq 1$ PD-1/PD-L1 Naïve
02	B2	SAR444245 + pembrolizumab	1-3L GC/GEJ non-MSI-H CPS $< 1$ PD-1/PD-L1 Naïve
02	B3	SAR444245 + pembrolizumab	2-4L GC/GEJ non-MSI-H - Regardless of CPS Post-PD1/PDL1
03	C	SAR444245 + pembrolizumab	2-3L post PD1/PDL1 HCC
04	D1	SAR444245 + pembrolizumab	3-6L mCRC non-MSI-H Any RAS
04	D2	SAR444245 + cetuximab	3-6L mCRC non-MSI-H RASwt

ESCC: esophageal squamous cell carcinoma; CPS: combined positive score; GC: gastric cancer; GEJ: gastro-esophageal junction adenocarcinoma, HCC: hepatocellular carcinoma; 1-3L: first to third line; 2-4L: second- to fourth-line; 2-3L: second to third line; 3-6L: third to sixth line; mCRC: metastatic colorectal cancer; MSI-H: high-level microsatellite instability; PD1/PDL1: programmed cell death 1 or programmed cell death-ligand 1; RASwt: RAS wild-type RECIST: response evaluation criteria in solid tumors;

After a screening period of up to 28 days, participants will receive treatment until progressive disease (PD), unacceptable adverse event (AE) or other full permanent discontinuation criteria (described in Section 7 of the master protocol) or completion of Cycle 35 (if applicable).

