### **3.6.1.2 SAR444245 exposure**

The dose information will be assessed by the following:

- Total number of cycles started per participant
- Duration of SAR444245 exposure (in months) is defined by (date of last administration of SAR444245 + 21 – date of first administration of SAR444245)/30.4375.
- Actual dose ( $\mu\text{g}/\text{kg}$ )
- Cumulative dose ( $\mu\text{g}/\text{kg}$ ): the cumulative dose is the sum of all actual doses of SAR444245, given from first to last administration
- Actual dose intensity (ADI in  $\mu\text{g}/\text{kg}/\text{week}$ ): defined as the cumulative dose divided by the duration of SAR444245 exposure (in weeks)
- Planned dose intensity (PDI in  $\mu\text{g}/\text{kg}/\text{week}$ ): corresponds to the planned dose at C1D1 divided by the theoretical cycle duration expressed in weeks (i.e. 3 weeks)
- Relative dose intensity (RDI, in %):  $100 \times \frac{\text{ADI } (\mu\text{g}/\text{kg}/\text{week})}{\text{PDI } (\mu\text{g}/\text{kg}/\text{week})}$

The total number of cycles started, number of cycles started by participant will be summarized by category. Duration of SAR444245 exposure, cumulative dose, ADI and RDI will be summarized quantitatively and by category if relevant.

The following variables will be derived to describe dose modifications and dose interruptions:

- Dose reduction: The first administration will not be counted as a dose reduction. For the second and subsequent SAR444245 administrations, dose reduction will be determined using the dose level intervals provided in [Table 7](#), by comparing the current dose level to the previous dose level. If the current dose level is below the dose level interval of the previous dose administration, then the current dose level is considered reduced.

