## 4 SAMPLE SIZE DETERMINATION

As the study is not intended to explicitly test a hypothesis, calculations of power and Type I error were not considered in the study design.

The plan is to treat approximately 40 participants in each cohort.

**Table 14** lists estimated ORR and 90% exact confidence intervals (CIs) by number of responders from a sample size of 40 participants treated.

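### The SAR444245 row splitting interruptions by 1st, 2nd and subsequent dose takes all doses started as its denominator, so its percentages are shares of all doses and not interruption risks at each dose position

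*SAP*

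**What the plan says.** The dose modification and interruption summaries for SAR444245 follow Table 7 in SAP section 3.6.1.2, in two blocks.

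- The participant block states its base: "number of participants treated will be used as denominator". It has no split by dose number.
- The dose block states a different base, once, for the whole list: "number of doses started will be used as denominator". Its rows cover all interruptions, those restarted or not, doses interrupted more than once, and "Number (%) of doses interrupted at 1st dose, 2nd dose, subsequent doses".

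An interruption is defined at the level of the single infusion: "A dose will be considered as interrupted if SAR444245 administration is stopped during an infusion regardless of whether it is restarted or not". The row split by dose number carries a percentage, and nothing in the section gives it a base other than the one at the head of the block.

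**The concern.** Only a first dose can be interrupted at the first dose. If those events are divided by all doses, the percentage depends on two things at once: how often the first infusion is interrupted, and how long participants stay on treatment. A reader who sees a split by 1st, 2nd and later doses is likely to read it as tolerability by infusion number, and these percentages do not answer that question.

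Two consequences follow. First, the first-dose percentage can change with no new first-dose event. Section 3.8 sets the primary cut-off at about 9 months after the last participant's first infusion and the final one at 18 months. All first doses have been given by the earlier date, but the total number of doses can still grow. Secondly, section 3.1 has results presented by cohort, and cohorts with different treatment durations would show different first-dose percentages even if the risk at the first infusion were the same.

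**Working it through.** The SAP gives no figure for this row, so there is nothing to reproduce. The relation can be derived exactly, and its size shown over a range.

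**Inputs from the SAP**
- Denominator for the row: all doses started (section 3.6.1.2).
- Cohort size: "The plan is to treat approximately 40 participants in each cohort" (section 4), so N = 40.
- Longest treatment: "completion of Cycle 35 (if applicable" (section 1.1), with planned dose intensity "divided by the theoretical cycle duration expressed in weeks (i.e. 3 weeks" (section 3.6.1.2). At one dose per cycle the mean number of doses cannot exceed 35.

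**Assumed, because the SAP does not give them**
- The mean number of SAR444245 doses per participant, m, and all interruption counts.

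**Formula.** Let N be first doses started, k1 the number of them interrupted, and D = N × m all doses started.
- Risk at the first dose: k1/N.
- Percentage under the stated denominator: k1/D = (k1/N)/m.
- Ratio of the two: D/N = m.

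The ratio is 1 only if nobody receives a second dose.

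**Range, with k1 = 8 and N = 40 (risk 8/40 = 20.0%)**

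| m | D | Row as stated, 8/D |
|---|---|---|
| 2 | 80 | 10.0% |
| 4 | 160 | 5.0% |
| 6 | 240 | 3.3% |
| 10 | 400 | 2.0% |
| 35 (ceiling) | 1,400 | 0.57% |

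**All three positions.** The divisor equals m only for the first dose. For the other positions it is D over the doses started at that position. Take an assumed cohort with 40 first, 32 second and 88 later doses (D = 160, m = 4) and 10, 4 and 6 interrupted.

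| Position | By position | As stated | Ratio |
|---|---|---|---|
| 1st | 10/40 = 25.0% | 10/160 = 6.3% | 4.0 |
| 2nd | 4/32 = 12.5% | 4/160 = 2.5% | 5.0 |
| Subsequent | 6/88 = 6.8% | 6/160 = 3.8% | 1.8 |

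The risk falls steadily by position, but as stated the later doses appear to be interrupted more often than the second. With a common denominator the order of the percentages is simply the order of the counts, and the last category pools many doses.

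A second assumed cohort behaves the same way. With 40, 30 and 120 doses (D = 190, m = 4.75) and 8, 3 and 6 interrupted, the risks are 20.0%, 10.0% and 5.0%, and the stated percentages are 4.2%, 1.6% and 3.2%.

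**Drift between cut-offs.** If D grew from 160 to 200 (assumed) with the same 10 first-dose events, the row would go from 10/160 = 6.3% to 10/200 = 5.0%. The first-dose risk would stay at 25.0%.

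**The case against.** The strongest reply is that the row is a breakdown and not a rate. It sits beneath the overall interruption row, among others that subdivide interrupted doses. With a common denominator, and each interrupted dose counted once, the parts add up: 6.25 + 2.5 + 3.75 = 12.5% = 20/160. Shares of interruptions can also be read correctly from it: 6.25/12.5 = 50%, which is 10 of 20. This stands. A reader might infer that the SAP understates a first-infusion interruption rate, or that the three percentages cannot be compared at all. The document supports neither. It never calls the row a risk per infusion or states its purpose, and the percentages are comparable as shares of all doses.

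It also stands that the counts are correct. First doses started equal the participants who received SAR444245, so 10/40 can be computed if that is the number shown as treated. Cycles started per participant, summarised by category, approximate the number of second doses. The safety analyses are descriptive (section 3.6), and no endpoint, futility rule or monitoring trigger in section 3.8 uses this row.

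Section 3.6.2 plans infusion reactions at the first and subsequent infusions by participant. That covers early-infusion tolerability, but it is a different variable and does not supply interruption by dose position.

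One could also read doses started as doses started at that position. The text does not say so, and if that is the intention it should be written down.

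**Conclusion.** The point holds as a weakness in a descriptive table. Under the denominator as written, the row gives shares of all doses. The first-dose percentage equals the first-dose risk divided by the mean number of doses per participant. That relation is exact. Its size is not known from the SAP, because the mean number of doses is not given, and every interruption count used here is an assumption. The order of second versus subsequent doses can reverse, as both assumed cohorts show, but need not.

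No other planned row gives interruption risk by dose position: the SAR444245 participant block has no such split, and the pembrolizumab and cetuximab summaries are by participant only. The impact is low. Nothing is miscounted, the first-dose risk is recoverable, and no decision rests on the figure. It is worth changing because the change costs almost nothing and makes the row informative about infusion number.

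**What to change.** In the dose block of section 3.6.1.2, state that the row split by dose number uses first doses started, second doses started and subsequent doses started as the respective denominators, and show each result as n/N (%). Keep all doses started as the base for the other rows.

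The cost is one line in the SAP and in the table shell, with no new data. The one loss is that the three percentages no longer sum to the overall interruption percentage, which is already reported in its own row. If the sponsor prefers the additive breakdown, labelling the row as a percentage of all doses started would at least prevent misreading, but it would not give the risk by position.

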### **3.6.1.3 Pembrolizumab exposure**

The dose information will be assessed by the following:

- Total number of cycles started per participant
- Duration of pembrolizumab exposure (in months) is defined by (date of last administration of pembrolizumab + 21 – date of first administration of pembrolizumab)/30.4375.
- Actual dose (mg)

- Cumulative dose (mg): the cumulative dose is the sum of all actual doses of pembrolizumab, given from first to last administration
- Actual dose intensity (ADI in mg/week): defined as the cumulative dose divided by the duration of pembrolizumab exposure (in weeks)
- Planned dose intensity (PDI in mg/week): corresponds to the planned dose at C1D1 and divided by the theoretical cycle duration expressed in weeks (ie, 3 weeks)
- Relative dose intensity (RDI, in %):  $100 \times \frac{\text{ADI (mg/week)}}{\text{PDI (mg/week)}}$

The total number of cycles started, number of cycles started by participants will be summarized by category. Duration of pembrolizumab exposure, cumulative dose, ADI and RDI will be summarized quantitatively and by category if relevant.

The following variables will be derived to describe dose modifications and dose interruptions:

- Dose omission is defined as a dose not administered at the scheduled visit.
- Dose interruption: A dose will be considered as interrupted if pembrolizumab administration is stopped during an infusion regardless of whether the infusion is restarted or not.

Dose modifications and dose interruptions will be analyzed by participant as follows:

- **Participant** (number of participants treated will be used as denominator)
  - Number (%) of participants with at least 1 dose modification
    - Number (%) of participants with at least 1 dose omission
    - Number (%) of participants with at least 1 dose interruption
      - Number (%) of participants with at least 1 dose interrupted and re-started
      - Number (%) of participants with at least 1 dose interrupted and not re-started
    - Number (%) of participants with at least 2 dose interruptions

### **3.6.1.4 Cetuximab exposure**

The dose information will be assessed by the following:

- Total number of cycles started
- Number of cycles started per participant
- Duration of cetuximab exposure (in months) is defined by (date of last administration of cetuximab + 7 – date of first administration of cetuximab)/30.4375.
- Actual dose (mg/m^2)
- Cumulative dose (mg/m^2): the cumulative dose is the sum of all actual doses of cetuximab, given from first to last administration

- Actual dose intensity (ADI in mg/m^2/week): defined as the cumulative dose divided by the duration of cetuximab exposure (in weeks)
- Planned dose intensity (PDI in mg/m^2/week): corresponds to the sum of planned dose started divided by theoretical duration of cetuximab exposure (in weeks)
- Relative dose intensity (RDI, in %):  $100 \times \frac{\text{ADI (mg/m}^2\text{/week)}}{\text{PDI (mg/m}^2\text{/week)}}$

The total number of cycles started, number of cycles started by participants will be summarized by category. Duration of cetuximab exposure, cumulative dose, ADI and RDI will be summarized quantitatively and by category if relevant.

The following variables will be derived to describe dose modifications and dose interruptions:

- Dose reduction: The first and second administration will not be counted as a dose reduction. For the third and subsequent cetuximab administrations, dose reduction will be determined using the dose level intervals provided in [Table 8](#), by comparing the current dose level to the previous dose level. If the current dose level is below the dose level interval of the previous dose administration, then the current dose level is considered reduced.

**Table 8 - Cetuximab dose reduction criteria**

Actual dose level	Dose level interval
250 mg/m 	> 225 mg/m 
Dose level -1 (200 mg/m  )	>175 mg/m  and ≤225 mg/m 
Dose level -2 (150 mg/m  )	>0 mg/m  and ≤175 mg/m 

- Dose omission is defined as a dose not administered at the scheduled visit.
- Dose interruption: A dose will be considered as interrupted if cetuximab administration is stopped during an infusion regardless of whether the infusion is restarted or not.

Dose modifications and dose interruptions will be analyzed by participant as follows:

- Participant** (number of participants treated will be used as denominator)
  - Number (%) of participants with at least 1 dose modification
    - Number (%) of participants with at least 1 dose reduction
    - Number (%) of participants with at least 1 dose omission
  - Number (%) of participants with at least 1 dose interruption
    - Number (%) of participants with at least 1 dose interrupted and re-started
    - Number (%) of participants with at least 1 dose interrupted and not re-started
  - Number (%) of participants with at least 2 dose interruptions

### 3.6.2 Adverse events

#### General common rules for adverse events

All AEs will be graded according to National Cancer Institute Common Terminology for Adverse Events (NCI-CTCAE version 5.0) and coded to a lower-level term (LLT), preferred term (PT), high-level term (HLT), high-level group term (HLGT), and associated primary system organ class (SOC) using the Medical Dictionary for Regulatory Activities (MedDRA) version currently in effect at Sanofi at the time of database lock. Cytokine Release Syndrome (CRS) and Immune effector cell associated neurotoxicity syndrome (ICANS) will be graded using ASTCT consensus grading.

The AEs will be analyzed in the following 3 categories:

- Pre-treatment AEs: AEs occurring during the pre-treatment period.
- Treatment-emergent adverse events (TEAE)s: AEs that developed, worsened (according to the Investigator's opinion) or became serious during the treatment-emergent period
- Post-treatment AEs: AEs that developed, worsened or became serious during the post-treatment period.

Similarly, the deaths will be analyzed in the pre-treatment, treatment-emergent and post-treatment periods.

The primary AE analyses will be on TEAEs. Pre-treatment and post-treatment AEs will be described separately.

An AE with incomplete or missing date/time of onset (occurrence, worsening, or becoming serious) will be classified as a TEAE unless there is definitive information to determine it is a pre-treatment or a post-treatment AE.

If the assessment of the relationship to IMP is missing for an AE, this AE will be assumed as related to IMP. Missing grade will be left as missing.

Multiple occurrences of the same event in the same participant will be counted only once in the tables within a treatment phase, using the maximum (worst) grade by treatment phase. Summaries will be provided for all grades combined and for grade  $\geq 3$  (including Grade 5). Missing grades, if any, will be included in the "all grades" category.

The AE tables will be sorted as indicated in [Table 9](#).

**Table 9 - Sorting of AE tables**

AE presentation	Sorting rules
SOC, HLGt, HLT and PT	By the internationally agreed SOC order and by alphabetic order of HLGts, HLTs and PTs.
SOC and PT	By the internationally agreed SOC order and decreasing frequency of PTs a,b
PT	By decreasing frequency of PTs a

---

- a Sorting will be based on the AE incidence.
- b The table of all TEAEs presented by primary SOC and PT will define the presentation order for all other tables (eg, treatment-emergent SAE) presented by SOC and PT, unless otherwise specified.

## **Analysis of all adverse events**

The overview of TEAE with the details below will be generated:

- Any TEAE
- Any grade  $\geq 3$  TEAE
- Any treatment-emergent SAE
- Treatment related TEAEs
- Treatment related TEAE of grade  $\geq 3$
- Serious treatment related TEAEs
- Grade 5 TEAE (any TEAE with a fatal outcome during the treatment-emergent period)
- Any TEAE leading to permanent full intervention discontinuation
- Any TEAE leading to permanent partial intervention discontinuation (discontinuation of each individual drug)

The AE summaries of **Table 10** will be generated with number (%) of participants experiencing at least one event. The analyses will be performed for all grades combined and for grades  $\geq 3$ . The all TEAE summary by Primary SOC and PT (and other safety summaries (eg, SAEs, deaths), if deemed needed after TEAE evaluation) will be performed by trial impact (disruption) due to COVID-19.

**Table 10 - Analyses of adverse events**

Type of AE	MedDRA levels
All TEAE	Primary SOC, HLGT, HLT and PT
TEAE related to IMP (overall) as per Investigator's judgment	Primary SOC and PT
Treatment emergent SAE	Primary SOC and PT
Treatment emergent SAE related to IMP (overall) as per Investigator's judgment	Primary SOC and PT
TEAE leading to permanent full intervention discontinuation	Primary SOC and PT
TEAE leading to permanent partial intervention discontinuation (for each individual drug)	Primary SOC and PT
TEAE leading to death (death as an outcome of the AE as reported by the Investigator in the AE page)	Primary SOC and PT
AE leading to death a	Primary SOC and PT
• In context of disease progression b	
• In context other than disease progression c	
Pre-treatment AE	Primary SOC and PT

Type of AE	MedDRA levels
Post-treatment AE	Primary SOC and PT
TEAE leading to dose interruption	Primary SOC and PT
TEAE leading to dose modification (including dose reduction, dose omission and cycle delay)	Primary SOC and PT

- a Death as an outcome of the AE as reported by the Investigator in the AE page
- b Death within 30 days from last IMP administration and the cause of death is disease progression
- c Death within 30 days from last IMP administration and for whom cause of death is not disease progression or the death occurred more than 30 days from last IMP administration and the cause of death is AE

### **Analysis of deaths**

In addition to the analyses of deaths included in [Table 10](#) the number (%) of participants in the following categories will be provided:

- Deaths during the treatment-emergent and post-treatment periods by main reason for death
- An overview of Grade 5 AEs will be provided with the following categories:
  - Grade 5 AE (TEAE and post-treatment).
  - Fatal TEAE (regardless of date of death/period).
    - Grade 5 TEAE with a fatal outcome during the treatment-emergent period,
    - Any Grade TEAE with a fatal outcome during the post-treatment period.
  - Post-treatment Grade 5 AE (excluding a TEAE that worsened to Grade 5 during the post-treatment period).

### **Analysis of adverse events of special interest (AESIs)**

Number (%) of participants experiencing at least one adverse event of special interest will be provided, by SOC and PT. The selection will be made using the eCRF specific **AESI** tick box. Tables will be sorted as indicated in [Table 9](#).

In addition, the following analyses will be done for infusion reaction category (selected by eCRF specific form) which are infusion related reactions (IRRs), cytokine release syndrome (CRS), flu-like symptoms (FLS) and anaphylaxis:

- Description of the infusion reaction category by predefined grouping and other reported PT.
- Worst grade
- Action taken for each IMP
- Corrective treatment given (Yes, No)
- Number (%) of participants with only 1 episode,  $\geq 2$ ,  $\geq 3$ ,  $\geq 4$  and  $\geq 5$  episodes
- Onset of first episode of infusion reactions (at the first infusion and subsequent infusions)

- Number (%) of participants with infusion reactions (any episode) at the first and subsequent infusions
- Number (%) of participants with at least one infusion with two episodes of infusion reactions
- Total number of infusion reaction episodes
- Time to onset from infusion (by category: Infusion day/ 1 day after infusion/ 2 to 3 days from infusion/ More than 3 days from infusion when applicable)
- Duration of infusion reaction (in days) (by category 1 day/ 2 to 3 days/ More than 3 days/Not recovered)
- Number (%) of participants with infusion reactions symptoms (as reported by investigator) by SOC and PT.

